#### ***Data analysis and statistics***

Different levels of comparisons will be done to explore the impact of the targeted phantom motor execution program on phantom phenomena and physical function of people with TTA. Before starting analyses, the normality of distribution of the quantitative variables will be assessed by the Shapiro-Wilk test. Since there are two groups of participants, whether participants are matched on their demographic and clinical characteristics will be explored using independent t-test and chi-square statistics. Based on our expectation of normality of distribution for the quantitative variables, if it is the case, parametric statistical tests will be used. An independent t-test will be used to compare quantitative variables within-subjects for the amputated and non-amputated sides. Similarly, Mann-Whitney test and Chi square test will be used respectively to compare ordinal and nominal categorical variables within-subjects for the amputated and non-amputated sides. An independent t-test will be analyzed to compare quantitative variables between the two groups. Similarly, Mann-Whitney test and Chi square test will be used respectively to compare ordinal and nominal categorical variables between the two groups.

Two-way analysis of variance can be used to compare the simultaneous effect of groups assignment and prosthesis embodiment on PLC. Similarly, Friedman's two-way analysis of variance will be used to compare the simultaneous effect of group assignment and surgical closure on PLC.

Spearman's correlation coefficients will be calculated to explore the potential relationship of phantom phenomena responses with participants' characteristics (i.e. age, weight, height, body mass index, length of the residual limb, the circumference of the residual limb, time after amputation, and years of prosthesis use). Moreover, the potential relationship of the phantom phenomena responses with participants' gender, type of surgery, and footedness will be explored by point-biserial correlation assessment. The potential

relationship of the phantom phenomena responses with participants' prosthesis type will be explored by partial eta square correlation assessment.

The linear regression analysis will be used to predict the effect of predictors / independent variables (i.e. clinical and demographic characteristics, and participants group) on outcomes / dependant variables (i.e. participants' physical function variables). Logistic regression analysis will be used to predict model of phantom phenomena based on participants' clinical and demographic characteristics, participants' group and physical function measures. Prior to regression analysis, regression assumptions including the normality, linearity, homoscedasticity (i.e. having equal variances in residuals of the predictors), and absence of multicollinearity (i.e. strong linear correlation between predictors as indicated by the average of the variance inflation factor (VIF) greater than 1) will be checked. For all statistical analyses, a p-value less than 0.05 will be considered statistically significant. The effect size and confidence intervals will be reported alongside other results to provide better judgment for the potential effects. All data will be analyzed offline using IBM SPSS software (Version 22.0, IBM Corp, New York, USA).

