### ***Experimental setup***

This research is a 2-arm, parallel, open label, non-blinded randomized controlled trial comprised of four independent but interrelated studies with the same participants. The familiarization phase, enrollment verification, obtaining verbal consent to participate, and gathering screening information will be done via phone interview. After screening participants, the Medical and Demographic Questionnaire will be administered. The participant will be e-mailed a link to complete the following surveys/questionnaires: Medical and Demographic questionnaire, Waterloo Footedness Questionnaire to determine their dominant lower extremity, and The Survey of Phantom Limb Awareness and Control that is a commonly used questionnaire regarding phantom phenomena. The participant can use a smartphone, iPad or computer to answer these surveys/questionnaires. Completion of the surveys/questionnaires at the home will respect COVID-19 restrictions by diminishing time spent with the researcher. If the participant is not able to complete the surveys/questionnaires prior to their first scheduled visit, they will be given the opportunity to do at WinPO prior to the physical function evaluation. At the conclusion of the phone interview, the researcher will randomly assign participants to the control or exercise groups. Participants in both groups will then be scheduled for an in-person baseline visit and an in-person follow up visit at WinPO for data collection. The baseline visit will begin with review of expectations and the participant will sign informed consent. All information gathered at the phone interview will be reviewed for accuracy. If the participant has not answered the questionnaires/surveys prior to their baseline visit, they will be provided an iPad to complete the Medical and Demographic Questionnaire, Waterloo Footedness Questionnaire, and The Survey of Phantom Limb Awareness and Control. The baseline testing session will be entirely the same for participants of both groups. During this session, the researcher will assess participants based on their anthropometric variables (i.e. height, weight, body mass index), the morphology of the residual limb (i.e. length, circumference, and volume),—prostheses embodiment as measured by TAPES-R and PEmbS-LLA, and functional abilities as measured by targeted phantom motor execution and FSST, while recording their muscle activities and plantar foot loads. After completion of the baseline testing, the researcher will contact [name], to get information with respect to what surgical closure technique was performed for the participant.

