### ***Experimental protocol***

At the beginning of the baseline testing session, the researcher measures participants' weight and height using a scale and stadiometer; the body mass index will be calculated using REDCap programmed formula. Then the researcher will survey prosthetic embodiment by asking participants to fill out the revised version of the Trinity Amputation and Prosthesis Experience Scales (TAPES-R) and Prosthesis Embodiment Scale for Lower Limb Amputees (PEmbS-LLA), which are brief self-administered questionnaires to assess the adjustment and interaction of people with amputation to their prosthesis. Then, the researcher will ask participants to sit on a chair within parallel bars and remove their prosthesis. The researcher will examine the residual limb and places paper skin markers on specific landmarks over their residual limb (i.e. middle of the patella, tibial tuberosity, the distal end of the residual limb). Then, participants will stand securely inside parallel bars while the researcher captures the shape of their residual limb using a 3D scanner (OMEGA Scanner 3D, Willow Wood, Ohio, USA). The morphologic characteristics of the residual limb (i.e. length, circumference, and volume) will be recorded. If the participant finds it difficult to stand without the prosthesis, the scan will be performed in sitting and note in the assessment. The participant will then return to the sitting position and placement for the electromyography (EMG) electrodes (Trigno, Delsys Inc., Massachusetts, USA) will be determined on both the intact and amputated limbs based on the standard electrode placement guideline. However, for the amputated side, since the length of the muscles has changed, the location of the EMG electrodes needs to be determined specifically for each participant based on the new muscle bulk and optimal electrical signal activity. Electromyography of the tibialis anterior, medial and lateral heads of the gastrocnemius muscle will be recorded for both sides. Electrode locations will be marked and photographed to ensure consistency with subsequent testing session recordings. The skin will be cleaned using an alcohol pad and electrodes will be attached using paper tape.

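### The amputated-versus-intact test sits under a statement about the programme's impact, but it has no group contrast and cannot show a programme effect; label it descriptive and add a between-arm contrast

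*Combined protocol and SAP*

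**What the plan says.** The section Data analysis and statistics opens with a general purpose: "Different levels of comparisons will be done to explore the impact of the targeted phantom motor execution program on phantom phenomena and physical function". After a normality check and a check that the groups match at baseline, it names a within-subject level of comparison: "An independent t-test will be used to compare quantitative variables within-subjects for the amputated and non-amputated sides". For the other variable types, "Mann-Whitney test and Chi square test will be used respectively to compare ordinal and nominal categorical variables within-subjects for the amputated and non-amputated sides". Neither sentence gives the session or the arm, and neither is labelled descriptive.

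A between-group level follows: "An independent t-test will be analyzed to compare quantitative variables between the two groups". The same section also puts group assignment into two-way analyses and into the regression models. One threshold covers everything: "For all statistical analyses, a p-value less than 0.05 will be considered statistically significant".

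Under Experimental setup, "This research is a 2-arm, parallel, open label, non-blinded randomized controlled trial", and all baseline measures are repeated at the second session. Under Experimental protocol, "Electromyography of the tibialis anterior, medial and lateral heads of the gastrocnemius muscle will be recorded for both sides". Muscle activity is therefore available on both limbs, at both sessions, in both arms. The same section notes that "for the amputated side, since the length of the muscles has changed, the location of the EMG electrodes needs to be determined specifically".

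**The concern.** The opening sentence gives the programme's impact as the purpose of the comparisons, and the side test has no other stated purpose. Yet that test asks whether two limbs of the same people are equal, which is a different hypothesis from the programme having no effect. Randomized group does not enter it, and as written neither does change between sessions.

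Amputation alone can make the limbs differ. A significant side difference after three weeks may then only restate a difference that was there before training. If training moves the amputated side toward the intact side, the same test becomes less likely to reject. Run at session 2 and read as evidence of impact, it could make a working programme look null and an inert one look significant.

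The bilateral recordings could answer a sharper question: did the side-to-side difference change more in the exercise arm than in the control arm? No planned analysis asks it. The between-group test includes group but does not use the intact limb as a reference.

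**Working it through.** **What the documents supply.** The threshold is 0.05 (sidedness not stated; two-sided assumed). The text supplied gives no sample size, standard deviation, side difference or correlation, so there is no planned figure to reproduce. The rest is illustration on assumed values.

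**Assumptions.** Normal outcomes with SD 1; n = 10, 20 or 30 per arm, equal allocation; between-side correlation r = 0.5; between-session correlation s = 0.7; amputated side lower than intact by D SD before training; the programme removes a share f of that deficit in the exercise arm only. The side test is run in the exercise arm at session 2. Both choices are mine, because the plan states neither. Simulation used 10,000 runs per setting.

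**Step 1: what the side test estimates.** At session 2 in the exercise arm the expected side difference is D(1 − f). With no effect (f = 0) it is D; with full restoration (f = 1) it is 0. The test's signal is therefore largest when the programme does nothing.

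**Step 2: rejection rates, D = 1 SD.**

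| n per arm | Side test | f = 0 | f = 0.5 | f = 1 |
|---|---|---|---|---|
| 10 | unpaired | 58.3% | 12.0% | 0.9% |
| 10 | paired | 80.6% | 29.3% | 5.0% |
| 20 | unpaired | 93.5% | 28.5% | 0.9% |
| 20 | paired | 99.0% | 56.0% | 5.4% |
| 30 | unpaired | 99.5% | 47.5% | 0.7% |
| 30 | paired | 100% | 75.2% | 5.0% |

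Pairing changes the level but not the direction. The unpaired test on paired limbs is a separate defect.

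**Step 3: dependence on the deficit, f = 0, at 10, 20 and 30 per arm.**
- D = 0.5: 11.4%, 28.8% and 47.7% unpaired; 29.3%, 55.8% and 75.0% paired.
- D = 0.2: roughly 2% to 5% unpaired. Paired, the SD of the side difference is √(2(1 − r)) = 1, so the noncentrality is 0.2√n = 0.63, 0.89 and 1.10, and the noncentral t gives about 9%, 14% and 19%.
- D = 0: about 1% unpaired and 5% paired.

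The problem shrinks with the deficit and disappears when there is none. From equal limbs, a programme effect would raise the rejection rate, not lower it.

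**Step 4: the contrast that does test the programme.** For each participant take (amputated − intact) at session 2 minus the same at session 1, and compare arms. With r = 0.5 and D = 1 it rejects about 5% when f = 0, and about 78%, 98% and 100% when f = 1 at 10, 20 and 30 per arm.

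**Step 5: its cost in precision.** The variance of amputated-side change is 2(1 − s) = 0.6. The variance of change in the side difference is 2(1 − r) × 2(1 − s). At r = 0.5 this is 1 × 0.6 = 0.6, the same, so nothing is gained or lost. At r = 0 it is 2 × 0.6 = 1.2, twice as large. Above r = 0.5 it is smaller. For comparison, at 20 per arm, D = 1, r = 0.5 and f = 1, a between-arm test of amputated-side change has 97.8% power and a follow-up-only test 87.2%.

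**The case against.** The strongest reply is that no misuse is written down. The opening sentence introduces the whole section, which also holds baseline matching tests and correlations with age and height that nobody would call impact tests. A reader might infer that the plan offers the side test as evidence of efficacy. The documents do not say so, and the between-group tests, the two-way analyses and the regressions with a group term do address impact. That stands: the fault is an unlabelled comparison, not a declared false efficacy test.

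A reader might also infer that the side test always rejects when the programme does nothing. That goes too far. It requires a real deficit, and the documents' only support is the altered muscle length, which concerns electrode siting and gives no size or direction for muscle activity. It also requires a session-2 analysis. At session 1 the test is legitimate description. Applied to change scores in the exercise arm (20 per arm, D = 1), it rejects 0.7% unpaired or 5.0% paired with no effect, and over 99% when the gap closes. The plan is silent on which is meant. Even on change scores, though, the test lacks the control arm and cannot separate the programme from whatever else changed over three weeks.

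Finally, limb symmetry is not a stated outcome in the text supplied, and the added contrast does nothing for measures without a side, such as the embodiment questionnaires or the step-test time. This is fair, and it is why the contrast belongs alongside the existing between-group comparison.

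**Conclusion.** The concern holds in a limited form. Whatever the data, a test of equal limbs without a group contrast cannot isolate a programme effect, and pairing does not change that. This needs no assumption.

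The misleading pattern is conditional on a sizeable pre-existing deficit, a session-2 analysis, and a programme that moves the amputated side toward the intact side. Under those conditions, at 20 per arm and r = 0.5, unpaired rejection falls from 93.5% with no effect to 0.9% with full restoration for a 1 SD deficit, and from 28.8% to 0.9% for 0.5 SD. With no deficit it stays at or below 5%. Sample size, deficit, correlations, sidedness and allocation ratio are all assumed.

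The plan's between-group analyses remain its route to impact. What needs correcting is the undefined role of the side test and the missing between-arm use of the bilateral data. The correction is cheap and should be made, but the trial does not stand or fall on it.

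**What to change.** In Data analysis and statistics:

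1. State that the amputated-versus-intact comparison describes asymmetry at session 1, with arms pooled and a paired analysis, and that it is not evidence of the programme's impact. Apply the same label and the same paired principle to the ordinal and nominal side comparisons.
2. For quantitative measures recorded on both limbs, add a between-arm comparison of the change from session 1 to session 2 in each participant's amputated-minus-intact difference. The session-2 difference adjusted for its session-1 value would also serve. Choose one in advance and report the estimate with its confidence interval.
3. Keep the existing between-group comparison; the new contrast supplements it.

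The cost is analysis wording only: no new data, visits or participants. The downside is the one in step 5: with equal variances, the contrast is noisier than amputated-side change alone when the two limbs' changes correlate below 0.5. Where they correlate at 0.5 it gains no power, and its value is that it answers the symmetry question directly.

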Physical function assessments will be done by performing targeted phantom motor executions and four-square step test (FSST). Muscle activity will be recorded for the targeted phantom motor executions while participants are not wearing their prosthesis. However, the assessment of FSST needs participants to wear their prosthesis without EMG recording. The justification for this decision is preventing the risk of injury at the skin-prosthesis interface due to electrodes and wires. Foot plantar load will be assessed during targeted phantom motor executions and FSST. Participants will rest 2 minutes while sitting in a chair after each physical function assessment (4 minutes in total). This time will be used to instruct the participant in the testing protocol. Additional time will be provided if requested by the participant. After baseline testing is complete, EMG electrodes and sensors for the foot plantar load will be removed. Participants will then be informed of their randomization group that was determined earlier (before their baseline assessment) using the block and simple randomization techniques.

Collected data for the morphology of the residual limb, phantom phenomena, TAPES-R, PEmbS-LLA, physical function assessments, and muscle activities of the first session are baseline data and will be used for comparison to the results of the same measurements of the second session. After the first session, participants in the exercise group will be enrolled in the targeted phantom limb exercise program in addition to continuing with their usual and customary post-amputation care while participants of the control group will continue with their usual and customary post-amputation care. Participants in the exercise group will be trained on the targeted phantom limb exercise program and will have specific training sessions for three weeks at participants' homes via Zoom (<https://zoom.us/>). The researcher will make Zoom video calls to supervise participants and get assurance that all instructions are followed. After three weeks, participants of both groups will attend the test center for the second testing session. For both testing sessions, the same researcher captures the shape of the residual limb, surveys the phantom phenomena, TAPES-R, and PEmbS-LLA, assesses physical function, and conducts EMG investigations.

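### Significance tests cannot show whether the randomised arms are balanced at baseline, and the between-arm tests are not adjusted for imbalance in named covariates

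*Combined protocol and SAP*

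**What the plan says.** The section headed Experimental setup describes a "2-arm, parallel, open label, non-blinded randomized controlled trial". Allocation is made "using the block and simple randomization techniques" (Experimental protocol).

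Under Data analysis and statistics, the plan states that "whether participants are matched on their demographic and clinical characteristics will be explored using independent t-test and chi-square statistics". The section ends with a common threshold: "For all statistical analyses, a p-value less than 0.05 will be considered statistically significant". It does not list the characteristics to be tested, and it does not say what follows from a significant or a non-significant result.

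The arms are then compared by independent t-test, Mann-Whitney test or chi-square test, according to the type of variable. No covariate enters these comparisons, and the baseline value of the outcome is not mentioned.

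The same section also plans linear regression of the physical function variables, and logistic regression of phantom phenomena. Both include clinical and demographic characteristics and group as predictors. Neither depends on the baseline test results. It promises effect sizes and confidence intervals alongside the other results.

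**The concern.** In a properly randomised trial, the null hypothesis of a baseline test is true by design: the two arms come from the same population. The test therefore cannot tell the reader what the word matched suggests. A small p-value marks a chance event. A large one may only mean that the trial is small. Neither measures how large the imbalance is or how strongly the characteristic predicts the outcome, and those two things decide whether the comparison is disturbed.

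What is at stake is the unadjusted between-arm comparison. If a prognostic characteristic happens to differ between arms, part of that difference carries into the estimated effect. The baseline test can still be non-significant and be read as reassurance. Because the plan ties no action to the tests, it also leaves open whether adjustment will be decided after the p-values have been seen.

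**Working it through.** The plan gives no error rate, power or sample size for these tests, so there is no stated figure to reproduce.

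**Inputs from the document**
- Threshold: 0.05 for every test. Two-sided testing is assumed.
- Number of characteristics: the balance tests have no list, so the correlation analyses in the same section serve as a proxy. They name 8 quantitative variables ("age, weight, height, body mass index, length of the residual limb, the circumference of the residual limb, time after amputation, and years of prosthesis use"), 3 binary ones ("gender, type of surgery, and footedness will be explored by point-biserial correlation assessment") and 1 more ("prosthesis type will be explored by partial eta square correlation assessment"), 12 in all.

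**Assumed inputs**
- Equal arms of n = 10, 15, 20 or 30, because the text available for review gives no sample size.
- Correlation rho = 0.5 or 0.7 between a baseline characteristic and the outcome.
- An observed imbalance d = 0.5 SD.

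**1. False flags across the table.** With k independent true-null tests, P(at least one p<0.05) = 1 - 0.95^k.
- k = 8: 33.7%
- k = 12: 46.0%, with 12 x 0.05 = 0.6 flags expected
- k = 14: 51.2%

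The characteristics are not independent. Body mass index is calculated from weight and height, and years of prosthesis use should follow time since amputation. A simulation of 12 characteristics at 20 per arm gave 46.5% when they were independent and 39% under assumed plausible correlations. Roughly 35-50% is a fair range for the table. The rate for any single test stays at 5%.

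**2. Smallest observed difference that is flagged.** A t-test reaches p<0.05 when the observed standardised difference is at least t(0.975; 2n-2) x sqrt(2/n).

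| n per arm | t | sqrt(2/n) | Threshold (SD) | z for d = 0.5 |
|---|---|---|---|---|
| 10 | 2.101 | 0.447 | 0.94 | 1.12 |
| 15 | 2.048 | 0.365 | 0.75 | 1.37 |
| 20 | 2.024 | 0.316 | 0.64 | 1.58 |
| 30 | 2.002 | 0.258 | 0.52 | 1.94 |

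At all four sizes an observed 0.5 SD difference is not flagged. At 50 per arm the threshold falls to 0.40 SD and at 64 to 0.35 SD, so there it would be flagged. A chance difference of at least 0.5 SD in either direction in one given characteristic, 2 x [1 - Phi(z)] with z from the table, has probability of about 26%, 17%, 11% and 5% at 10, 15, 20 and 30 per arm.

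**3. Effect on the unadjusted comparison.** Given the imbalance, and with no treatment effect, the expected outcome difference is rho x d: 0.5 x 0.5 = 0.25 SD and 0.7 x 0.5 = 0.35 SD. The conditional standard error is s = sqrt(1 - rho^2) x sqrt(2/n). The unadjusted test rejects beyond c = 1.96 x sqrt(2/n). By normal approximation, the conditional type I error is 1 - Phi((c - rho d)/s) + Phi((-c - rho d)/s).

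For n = 20 and rho = 0.5: c = 0.620 and s = 0.274. The upper term is 1 - Phi(1.350) = 0.0885 and the lower term is Phi(-3.176) = 0.0007, which gives 0.089.

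| n per arm | rho = 0.5 | rho = 0.7 |
|---|---|---|
| 10 | 0.055 | 0.050 |
| 15 | 0.072 | 0.080 |
| 20 | 0.089 | 0.116 |
| 30 | 0.126 | 0.199 |

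At 10 per arm there is essentially no inflation. From 15 to 30 per arm it rises from 7-8% to 13-20%, while the baseline test remains non-significant.

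**The case against.** Five objections deserve weight.

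- **The plan only explores matching.** It ties no decision to the result. A reader might infer that it will declare the arms matched, or choose covariates by p-value. The document says neither, so deleting the tests would by itself change no estimate. This stands. The harm from the tests is to interpretation, and the gain comes from adjustment.
- **Adjusted models are already planned.** The regressions on characteristics and group do not depend on baseline p-values, and effect sizes and confidence intervals are promised. This stands in part. The models name no specific covariates, do not mention the baseline outcome, are framed as prediction, and are not said to replace the unadjusted tests. Equally, nothing calls the t-test the main analysis, so it should not be described as such.
- **Chance imbalance does not bias a randomised comparison.** This is correct on average over randomisations. The distortion is conditional on the imbalance that occurs. A reader might infer that the trial result will be biased, and the documents do not support that.
- **Half of all tests giving a false alarm would be a misreading.** The 35-50% is a whole-table figure on an assumed list. Nor should the power to detect a true 0.5 SD population difference be used here: under randomisation that difference is zero, so the relevant figure is the threshold for an observed imbalance.
- **Baseline differences may not be pure chance.** The plan says that "At the conclusion of the phone interview, the researcher will randomly assign participants to the control or exercise groups". This comes before signed consent and baseline testing, and no concealment is described. Selection or drop-out could therefore create real differences. This is why the argument is conditional on sound allocation. Significance tests in a small trial would be a weak check for that problem too.

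**Conclusion.** The point holds in a limited form. Significance tests at 0.05 do not answer whether the randomised arms are balanced. That conclusion needs no sample size, only sound allocation. The false-flag figure depends on how many characteristics are tested and how correlated they are.

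The effect on the unadjusted comparison depends on the sample size and on correlations that the document does not supply. Up to about 30 per arm, a 0.5 SD imbalance passes unflagged. If the characteristic is correlated 0.5 to 0.7 with the outcome, the conditional type I error lies between about 5% (10 per arm) and 13-20% (30 per arm). At 50 per arm or more, an imbalance of that size would be flagged and this part of the argument is much weaker. No listed characteristic is shown in the document to be that prognostic.

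The planned regressions reduce the problem but do not settle it while their covariates and their standing relative to the unadjusted tests are unstated. The point is worth acting on because adjustment for data already collected costs almost nothing.

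**What to change.** Under Data analysis and statistics:

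1. Remove the baseline t-tests and chi-square tests. Tabulate each characteristic by arm (mean and SD, or counts) with the standardised difference.
2. Make the between-arm comparison a regression or ANCOVA with group, the baseline value of the outcome, and one or two prognostic characteristics named in advance, for example time since amputation. Include them whatever their observed balance.
3. State that this model gives the treatment effect estimate, and how the unadjusted tests and the planned prediction regressions relate to it.
4. State that no covariate will be added or dropped because of a baseline p-value.

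The cost is SAP wording and one degree of freedom for each covariate that enters as a single term: 1 + 1 = 2 or 1 + 2 = 3 in all, of which one or two are for the prognostic characteristics. No new data are needed, because baseline measures and characteristics are already collected. Adjustment for covariates that do predict the outcome also improves precision.

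### Amputated and intact limbs of the same participant are compared with tests for independent samples, which ignore the pairing

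*Combined protocol and SAP*

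**What the plan says.** The section on data analysis and statistics plans a comparison of the two limbs and calls it within-subjects. For quantitative variables: "An independent t-test will be used to compare quantitative variables within-subjects for the amputated and non-amputated sides". For the other variable types: "Mann-Whitney test and Chi square test will be used respectively to compare ordinal and nominal categorical variables within-subjects for the amputated and non-amputated sides".

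The experimental protocol confirms that both limbs of each participant are measured: "Electromyography of the tibialis anterior, medial and lateral heads of the gastrocnemius muscle will be recorded for both sides".

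The analysis section then gives the same three tests to the comparison of exercise with control, beginning: "An independent t-test will be analyzed to compare quantitative variables between the two groups". There they are the right type of test, because the groups consist of different people.

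Two general rules carry over to the side comparison: "For all statistical analyses, a p-value less than 0.05 will be considered statistically significant", and "The effect size and confidence intervals will be reported alongside other results".

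**The concern.** The independent t-test, Mann-Whitney and chi-square tests all assume that the two samples are independent. Here each participant supplies one value to each sample, so independence fails by design. The plan recognises the pairing in its description and then chooses tests that discard it.

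The direction of the error depends on the correlation between limbs:

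- **Positive correlation**, the usual expectation for two limbs of one person: the standard error is too large, p-values are too high, intervals are too wide, and real side differences are missed.
- **Negative correlation**: the standard error is too small and the false-positive rate exceeds 5%.

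Since the plan promises confidence intervals as well as p-values, both are affected.

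**Working it through.** **Is a paired method named elsewhere?** The analysis section names no paired t-test, Wilcoxon signed-rank test, McNemar test or mixed model. Friedman's test is the only repeated-measures method named, and it is assigned to group assignment and surgical closure, not to sides. All three tests named for sides are unpaired, so a slip in a single word is unlikely.

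**Inputs.** From the plan: significance level 0.05 (sidedness not stated; two-sided assumed). Not given in the reviewed text, hence assumed: n participants, between-limb correlation ρ, a common SD σ on both sides, and a true side difference of 0.5 SD for power. The plan gives no figure for this comparison that could be reproduced.

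**Formulas.**

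- True variance of the mean side difference: 2σ²(1 − ρ)/n.
- Variance used by the independent t-test: 2σ²/n.
- Ratio of interval width to correct width (large sample): 1/√(1 − ρ).
- Actual two-sided type I error (large sample): 2·[1 − Φ(1.96/√(1 − ρ))].

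For ρ = 0.5, the width ratio is 1/√0.5 = 1.41. The critical value becomes 1.96/0.707 = 2.77, so the type I error is 2·[1 − Φ(2.77)] = 0.0056. For ρ = −0.3, the critical value is 1.96/√1.3 = 1.72 and the type I error is 0.086.

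**Simulation at n = 20.** Bivariate normal data, 40,000 replicates for the t-tests and 4,000 for Mann-Whitney:

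| ρ | Type I, formula | Type I, independent t | Type I, Mann-Whitney | Width ratio (large sample) | Power, independent t | Power, paired t |
|---|---|---|---|---|---|---|
| −0.3 | 0.086 | 0.084 | 0.083 | 0.88 | 0.36 | 0.26 |
| 0 | 0.050 | 0.050 | 0.048 | 1.00 | 0.34 | 0.32 |
| 0.3 | 0.019 | 0.022 | 0.022 | 1.20 | 0.31 | 0.43 |
| 0.5 | 0.006 | 0.007 | 0.007 | 1.41 | 0.28 | 0.56 |
| 0.7 | 0.0003 | 0.0008 | 0.0008 | 1.83 | 0.25 | 0.78 |

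At ρ = −0.3 the independent test's higher power is not a gain, because its type I error is above 5%.

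**Other sample sizes.** The pattern holds at n = 10, 30 and 40. At ρ = 0.5, power of the independent against the paired t-test is 0.12 against 0.29 (n = 10), 0.47 against 0.75 (n = 30) and 0.63 against 0.87 (n = 40). The paired t-test kept its type I error between 0.048 and 0.052 at every n and ρ tried.

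**Nominal data.** Chi-square was not simulated, but the reasoning is the same. A table of side by category counts each participant twice and treats the 2n limbs as 2n independent observations.

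**The case against.** Four points can be made on the other side.

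1. **The trial's main question is not touched.** The effect of the exercise programme is judged by exercise against control, for which the plan assigns independent-samples tests. The side contrast is not randomised, and the reviewed text does not make it a primary outcome. This stands and limits the scope. It does not make the side tests valid.

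2. **Few measures are clearly two-sided.** Only EMG of three muscles is expressly recorded on both limbs. Morphology is taken on the residual limb, the embodiment questionnaires and the step test are person-level, and plantar load is not said to be two-sided. This stands for the data: no ordinal or nominal two-sided variable can be identified. But the plan itself prescribes side comparisons for all three variable types, so the text needs correcting for all three.

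3. **The error may be smaller than shown.** The figures assume equal SDs, and muscle on the amputated side is altered, with electrodes placed individually. With SD ratio k, the large-sample width ratio is √[(1 + k²)/(1 + k² − 2ρk)]. For k = 2 and ρ = 0.3, 0.5, 0.7 it is √(5/3.8) = 1.15, √(5/3) = 1.29 and √(5/2.2) = 1.51, and simulated type I error at n = 20 is about 2.6%, 1.6% and 0.5%. For k = 3 the width ratios are 1.10, 1.20 and 1.31, and type I error is about 3.4%, 2.7% and 1.4%. Even with equal SDs, the independent test has 38 degrees of freedom and the paired test 19, which brings the ratios at n = 20 to about 1.16, 1.37 and 1.77. All of this trims the size and leaves the direction unchanged.

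4. **With positive correlation the error is conservative.** It costs power and does not create false claims. That is true for ρ > 0, but the plan gives no basis for knowing the sign for every measure, and intervals that are too wide are still wrong.

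**Conclusion.** The concern holds. The plan describes a paired comparison and assigns it three tests for independent samples, and nothing else in the text corrects this.

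The size is illustrative, since neither the sample size nor the correlation is given. At ρ = 0 the independent t-test is essentially correct. Under equal SDs the loss grows quickly with positive correlation: at ρ = 0.5 and n = 20 its power for a 0.5 SD difference is half that of the paired test (0.28 against 0.56). Unequal SDs reduce the loss.

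The defect is confined to the side-to-side comparisons, documented in the plan for EMG. Within that scope it must be corrected, because the named tests are invalid by design for a prespecified analysis.

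**What to change.** In the section on data analysis and statistics, replace the tests named for the amputated-versus-intact comparison:

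- **Quantitative variables:** paired t-test, with normality checked on the within-participant side differences. Use the Wilcoxon signed-rank test if those differences are clearly non-normal.
- **Ordinal variables:** Wilcoxon signed-rank test.
- **Nominal variables:** McNemar's test, or McNemar-Bowker for more than two categories.

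A mixed model with side as a within-participant factor is an acceptable alternative for the quantitative measures. Report effect sizes and confidence intervals on the paired differences. List the variables actually measured on both limbs, so that it is clear where these tests apply. Keep the independent-samples tests for the comparison between randomised groups only.

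The cost is a few sentences. The replacement tests are available in the SPSS package that the plan names, and no further data are needed. The change should be made before the data are analysed, so that the choice of test does not follow the results.
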